1.1 Background and Rationale

Absolute myocardial blood flow (MBF) and myocardial flow reserve (MFR) using positron emission tomography (PET) provide additional diagnostic and prognostic power compared to relative perfusion results [1-7]. Myocardial perfusion imaging is much more widely carried out with single photon emission tomography (SPECT) than with PET. However, measurements of MBF or MFR are rarely obtained with SPECT due to technical reasons (need for attenuation and scatter correction and the requirement of the camera to rotate around the patient for 3-dimensional imaging). An estimate of MFR without a direct measurement of MBF can be determined with a combination of dynamic planar followed by static SPECT acquisitions [8] and provides useful prognostic information [9]. Dynamic tomographic data can be acquired with rapid rotation of SPECT camera and provide 1) a measure of MFR [10] and 2) the arterial input function [11] suggesting that accurate measures of MBF could be possible with SPECT [12].

The recent development of dedicated solid state cardiac SPECT cameras has made the possibility of MBF measurement much more feasible and practical. Cameras such as the NM 530c/570c cameras (GE Healthcare, Haifa, Israel) and the DSPECT system (Spectrum Dynamics Medical Inc., Palo Alto, CA) have greatly improved sensitivity and are stationary [13]. These features allow dynamic imaging with high temporal resolution and improved count density and facilitate MBF measurement with SPECT. Recent work has shown the capability to provide an index of global MFR [14], but no studies have demonstrated measurement of MBF.

For the first time, [name] and our group recently demonstrated the accurate quantification of MBF in a pig model of rest and transient occlusion at stress [15]. Data were acquired using attenuation and scatter corrected dynamic SPECT data with a NM 530c camera with ^{201}TI , $^{99\text{m}}\text{Tc}$ -tetrofosmin and $^{99\text{m}}\text{Tc}$ -sestamibi. MBF was measured with gold-standard microspheres injected simultaneously with the SPECT tracers. Measured extraction fraction data agreed with those obtained previously using invasive techniques. MBF determined using the measured extraction fractions produced accurate values and good correlations with microsphere MBF between $r=0.75$ and $r=0.83$ ($p<0.01$ for all) and the resulting correlation in the MFR was up to 0.89 ($p<0.01$). Thus, non-invasive measurement of absolute MBF with a stationary dedicated cardiac SPECT is feasible using common perfusion tracers.

The goal of this study is to compare SPECT and PET measurement of MBF and MFR and determine the reproducibility of SPECT MFR measurements in patients.

1.2 Hypothesis

1. The correlation of global and regional myocardial blood flow (MBF) measurements and calculated myocardial flow reserve (MFR) using SPECT to PET in participants with an intermediate to high probability of CAD will be $r > 0.6$ (Phase 1);
2. The test-retest reproducibility of global and regional MBF measurements and calculated MFR using SPECT in participants with an intermediate to high probability of CAD will be within 10 to 15% (Phase 2);
3. The correlation of global and regional MBF measurements and calculated MFR using SPECT to PET in normal volunteers will be $r > 0.6$ (Phase 3).

2. Study Objectives

1. To evaluate the correlation of global and regional MBF and MFR measured using SPECT to that measured using PET in participants with an intermediate to high probability of CAD (Phase 1);
2. To determine the reproducibility of global and regional MBF measurements and calculated MFR using SPECT in participants with an intermediate to high probability of CAD (Phase 2);
3. To evaluate the correlation of global and regional MBF and MFR measured using SPECT to that measured using PET in normal volunteers (Phase 3).

3. Study Design

Phase 1:

Patients referred to the University of Ottawa Heart Institute Diagnostic Imaging Department for myocardial perfusion imaging (MPI), PET or SPECT, will undergo a clinically indicated rest/stress PET scan using either Rb-82 or $^{13}\text{NH}_3$. Research imaging will consist of a rest/stress SPECT scan with $^{99\text{m}}\text{Tc}$ completed with 4 weeks of the PET scan, occurring either before or after the PET scan.

Study end will be defined as the completion of both the PET and SPECT scans.

Phase 2:

Patients will undergo a clinically indicated rest/stress SPECT scan as referred. Research imaging will consist of a second rest/stress SPECT scan with $^{99\text{m}}\text{Tc}$ within 4 weeks of the clinical SPECT scan.

Study end will be defined as the completion of both SPECT scans.

Phase3:

Normal volunteers will undergo a rest/stress PET scan using either Rb-82 or $^{13}\text{NH}_3$ and a rest/stress SPECT scan with $^{99\text{m}}\text{Tc}$ completed within a 4 week period.

Study end will be defined as the completion of both the PET and SPECT scans.

4. SPECT and PET Imaging

4.1 $^{99\text{m}}\text{Tc}$ SPECT Imaging

The camera used in this study will be the Discovery NM 530c (GE Healthcare, Haifa, Israel). This camera is a dedicated cardiac camera that uses 19 cadmium-zinc-telluride (CZT) based detectors [16]. Each detector is 8 x 8 cm divided into a 32x32 array with a pixel pitch of 2.46mm. Each detector has a single-pinhole collimator with an effective diameter of 5.1mm. The detectors are arranged in an arc around the field-of-view, providing sufficient angular sampling for 3D reconstruction without the need to rotate the camera. The sensitivity of the system is approximately 4-times higher than a standard dual-head gamma camera.

Participants will be instructed to fast for a minimum of 4 hours and to abstain from products containing caffeine for 24 hours prior to imaging.

$^{99\text{m}}\text{Tc}$ -tetrofosmin (370 MBq (2.8 mSv) for rest and 1100 MBq (7.7 mSv) for stress) will be delivered using a power injector as a 9 ml bolus over 30 s followed by a 9 ml saline flush over 30 s. Image data will be acquired in listmode for 11 min starting just prior to tracer injection. Resting images will be acquired first and repeated just prior to stress. For stress, dipyridamole (0.14 mg/kg/min over 5 min) will be given intravenously. At 8 minutes following onset of dipyridamole infusion, stress imaging will start prior to the $^{99\text{m}}\text{Tc}$ -tetrofosmin injection. Aminophylline will be administered intravenously at 11 minutes following onset of dipyridamole infusion. The usual post-stress images will be acquired approximately 45 minutes after radiotracer injection.

Following acquisition, the listmode data will be rebinned into 9x10s, 6x15s, 4x120s frames. The projection data for each frame will be independently reconstructed using manufacturer supplied MLEM iterative reconstruction that includes point-spread function modeling and a noise-suppression prior. A total of 30 iterations will be used corresponding to the manufacturer recommendation for resting (low-count) studies. Images will be filtered post-reconstruction using a 3D 5th-order Butterworth filter with a cut-off frequency of 0.37 cycles/cm. Images will be reconstructed without corrections (NC), and with attenuation correction (AC) and scatter correction (SC). When applied, AC will be based on the CT scan from the PET/CT acquisition which will be coregistered manually to the emission reconstruction using on-line quality assurance tools. SC will be applied to the projection data prior to reconstruction using a dual-energy window approach [15]. For the Phase 2 SPECT reproducibility study, an additional CT scan will be acquired on an Infinia/Hawkeye 4 SPECT/CT gamma camera and used in place of the CT from the PET/CT acquisition.

The reconstructed dynamic image series will be processed using FlowQuant (Ottawa, ON), our in-house kinetic analysis software [17] as well as Infinia (GE Canada). With this semi-automatic software, a 1-tissue-compartment model will be fit to the myocardium time-activity data to generate a parameterized map of the uptake rate constant K1 (ml/min/g) for the heart. K1 values will be scaled to MBF based on the K1-MBF relationship determined from the pig studies (15). Finally, the results from the FlowQuant (Ottawa, ON) will be compared to those of the commercially released Infinia software (GE Canada) to determine the similarities between the two software packages.

4.2 ^{82}Rb / $^{13}\text{NH}_3$ PET Imaging

Rb-82 or $^{13}\text{NH}_3$ PET Imaging will be performed according to the UOHI standard clinical protocol [18]. Briefly, the participants will be positioned in a 3D PET system (GE Discovery 690 PET/VCT). The initial rest PET scan will include a low-dose CT for attenuation correction (0.4 mSv; fast helical 2 s, 120 kVp with axial and angular mA-modulation at noise-index = 50). Hyperemic stress flow will be induced with dipyridamole (0.14 mg/kg/minute for 5 minutes). PET imaging will be performed using 1000 MBq (0.73 mSv) of Rb-82 or 3 MBq/kg (0.7 mSv) of $^{13}\text{NH}_3$ at rest and during stress with radiotracer injected 8 minutes following the start of dipyridamole infusion. MBF and MFR will be quantified and polar-maps generated for each rest and stress state using in-house FlowQuant[®] software [17] as well as Infinia (GE Canada).

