2. To determine the reproducibility of global and regional myocardial blood flow measurements and calculated myocardial flow reserve using SPECT and ^{99m}Tc -tetrofosmin in patients with an intermediate to high probability of CAD (Phase 2);
3. To evaluate the correlation of global and regional myocardial blood flow measurements and calculated myocardial flow reserve using SPECT and ^{99m}Tc -tetrofosmin to PET with Rb-82 or $^{13}\text{NH}_3$ in normal volunteers (Phase 3).

Hypotheses

1. The correlation of global and regional myocardial blood flow measurements and calculated myocardial flow reserve using SPECT to PET in patients with an intermediate to high probability of CAD will be $r > 0.6$ (Phase 1);
2. The test-retest reproducibility of global and regional myocardial blood flow measurements and calculated myocardial flow reserve using SPECT in patients with an intermediate to high probability of CAD will be within 10 to 15% (Phase 2);
3. The correlation of global and regional myocardial blood flow measurements and calculated myocardial flow reserve using SPECT to PET in normal volunteers will be $r > 0.6$ (Phase 3).

Study Type

Investigator-initiated, imaging research.

Study Design

For the Phase 1 correlation study, participants will undergo a standard clinical rest/stress PET study with either Rb-82 or $^{13}\text{NH}_3$ with a low dose CT and a rest/stress SPECT study with $^{99\text{m}}\text{Tc}$ within a 4 week period. Participants with CAD will be recruited from patients already referred for clinical SPECT or PET imaging and with an intermediate to high probability of CAD. Any participants who have an intervention or undergo a significant cardiac event during the 4 week interval will be excluded.

For the Phase 2 reproducibility study, participants will be recruited from patients already referred for clinical rest/stress SPECT imaging and with an intermediate to high probability of CAD. Participants will undergo a second rest/stress SPECT with $^{99\text{m}}\text{Tc}$ within a 4 week period. Any participants who have an intervention or undergo a significant cardiac event during the 4 week interval will be excluded.

For the Phase 3 correlation study, normal volunteer participants will undergo a standard rest/stress PET study with either Rb-82 or $^{13}\text{NH}_3$ with a low dose CT and a rest/stress SPECT study with $^{99\text{m}}\text{Tc}$ within a 4 week period.

Number of Participants

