Statistical Methods For the correlation studies, global and regional MBF measurements acquired using SPECT and PET and calculated MFR measurements will be correlated with Spearman correlation analysis. For the reproducibility study, Bland-Altman plots will be used to determine significant bias and the coefficient of repeatability of global and regional MBF measurements acquired using SPECT and calculated MFR.

Abbreviations

3D	three dimensional
ACC	American College of Cardiology
AC	attenuation correction
AE	Adverse Event
AV	atrial-ventricular
BMI	body mass index
CABG	coronary artery bypass graft
CAD	coronary artery disease
CRF	case report form
COPD	chronic obstructive pulmonary disease
CT	computed tomography
g	gram
ICH GCP	International Conference on Harmonization Good Clinical Practice
kg	kilograms
kVp	kilo-volt potential
MBF	myocardial blood flow
MBq	megabequerels
mcg	micrograms
mCi	millicurie
MFR	myocardial flow reserve
mg	milligrams
min	minute
mm	month
MRN	medical record number
mSv	milliseverts
¹³ NH ₃	Nitrogen-13-ammonia
NC	no correction
NYHA	New York Heart Association
OHSN-REB	Ottawa Health Science Network Research Ethics Board
PET	positron emission tomography
PCI	percutaneous coronary intervention
PHI	Personal Health Information
⁸² Rb	Rubidium-82 Chloride
SAE	Serious Adverse Event
SC	scatter correction
SPECT	single photon emission computed tomography
SOP	Standard Operating Procedures
^{99m} Tc	Technetium-99m
²⁰¹ Tl	Thallium Chloride
TOH	The Ottawa Hospital
UOHI	University of Ottawa Heart Institute
yyyy	year

1. Introduction

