4.3 Concentration of $^{99\text{m}}\text{Tc}$ SPECT tracer

SPECT perfusion tracers are known to bind to red blood cells limiting the amount of tracer available to the myocardium for extraction [15]. Thus, concentration function used in the kinetic analysis is better represented by the plasma concentration of tracer instead of the whole blood concentration, as measured by the image-based methods used in this study. Correction for the plasma to whole blood ratio can be done by applying a correction curve. The correction curve has been determined with pig experiments but needs to be calibrated to humans. To estimate this correction, we will measure the whole-blood to plasma tracer concentration ratio at equilibrium (~30min post injection) which will then be used to rescale the full curve that was measured in the pig study. For this purpose, a 12ml blood sample (2x6ml) at 30min after the rest tracer injection and a 2nd 12ml (2x6ml) blood sample at 30min will be drawn after the stress injection. Whole blood and serum aliquots will be prepared and then measured in a well-counter to determine the concentration ratio.

5. Sample Size and Statistical Analysis

The sample size for the correlation studies (hypotheses 1 and 3) was calculated to provide a 95% confidence interval around $r=0.6$ that excludes $r=0.25$, which is considered the upper bound of no correlation. To obtain a difference in the z-transform of $r=0.6$ and $r=0.25$ of 1.96 requires an n of 24. A withdrawal rate of 10 to 15 % increases the number of patients required to 30 per group.

The sample size for the reproducibility study (hypothesis 2) is estimated to detect a 10% difference on background of 15% variability (assuming a SPECT MBF uncertainty similar to the high end of PET variability). This requires a sample size of 26 (power = 0.95; alpha =0.05). A withdrawal rate of 10 to 15 % increases the number of patients required to ~ 30 per group.

Adverse events will be listed on an individual basis. All safety variables and demographic data will be tabulated with descriptive statistics, if appropriate.

For the correlation studies global and regional MBF measurements acquired using SPECT and PET and calculated MFR will be correlated with Spearman correlation analysis. For the reproducibility study Bland-Altman plots will be used to determine significant bias and the coefficient of repeatability of global and regional MBF measurements acquired using SPECT and calculated MFR.

6. Study Population

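### Hypothesis 2 sets a 10 to 15% reproducibility limit without naming the statistic, and the stated 0.95 power is power to detect bias, not power for repeatability

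*Combined protocol and SAP*

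**What the plan says.** Section 1.2 states hypothesis 2 as a range: test-retest reproducibility of global and regional MBF and of MFR "in participants with an intermediate to high probability of CAD will be within 10 to 15% (Phase 2"). The Synopsis has the same range: "in patients with an intermediate to high probability of CAD will be within 10 to 15% (Phase 2"). Neither place says whether the percentage is a mean bias, a within-subject coefficient of variation (CV), an SD of differences or a CR, or which end of the range decides.

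The analysis is given in the Synopsis (Statistical Methods): "Bland-Altman plots will be used to determine significant bias and the coefficient of repeatability of global and regional MBF measurements acquired using SPECT". Section 5 repeats it. No acceptance limit is attached to either output.

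Section 5 sizes the study for hypothesis 2. The number is "estimated to detect a 10% difference on background of 15% variability", where the variability is chosen by "assuming a SPECT MBF uncertainty similar to the high end of PET variability". "This requires a sample size of 26 (power = 0.95; alpha =0.05"), and withdrawals raise it to about 30. The paragraph does not say whether the test is one- or two-sided, or whether the 15% is the SD of paired differences or the error of a single scan.

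**The concern.** Phase 2 exists to establish how repeatable SPECT flow measurements are. Its hypothesis is about spread, but detecting a 10% difference is a statement about the mean. A reader who sees power 0.95 beside hypothesis 2 may take it as assurance about repeatability.

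A bias test cannot supply that assurance. With no true bias, a 5% test is non-significant 95% of the time however widely the two scans differ within patients. Because the statistic is not named, the limit could also be applied after the data are seen to whichever measure of spread happens to satisfy it.

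**Working it through.** **Inputs.** Difference 10%, variability 15%, power 0.95, alpha 0.05 and n = 26 come from Section 5. The paired design (two SPECT scans per patient) comes from Section 3. Assumptions not in the documents: percent differences are roughly normal, and CR = 1.96 × SD of differences.

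**1. Reproducing n = 26.** Paired t-test on the mean difference, with noncentrality (10 / SD of differences) × √n.

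| Reading of the 15% | Sides | Power at n = 26 | n for 0.95 |
|---|---|---|---|
| SD of differences = 15 | one | 0.952 | 26 |
| SD of differences = 15 | two | 0.904 | 32 |
| Per-scan error: SD of differences = 15 × √2 = 21.2 | one | 0.756 | 51 |
| Per-scan error: SD of differences = 21.2 | two | 0.637 | 61 |
| CR itself: SD of differences = 15 / 1.96 = 7.65 | one / two | above 0.99 | 8 / 10 |

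At n = 25 the first row gives 0.944, so 26 is the smallest number that reaches 0.95. An unpaired comparison would need 49 (one-sided) or 59 (two-sided) per arm. Of the readings tried, only the first row returns 26 at the stated power and alpha. A two-sided test also gives 26, but at power 0.90. The allowance for withdrawals is consistent: 26 / 0.90 rounds up to 29 and 26 / 0.85 to 31.

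**2. How the candidate statistics relate.** SD of differences = √2 × within-subject CV, and CR = 1.96 × SD of differences = 2.77 × CV.

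- If 15% is the SD of differences: CV = 15 / √2 = 10.6% and CR = 1.96 × 15 = 29.4%.
- If 15% is per-scan error: CV = 15%, SD of differences = 21.2% and CR = 41.6%.
- In reverse, a CR of 15% needs an SD of differences of 15 / 1.96 = 7.7% (CV 5.4%), and a CR of 10% needs 5.1% (CV 3.6%).

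**3. How far the choice of statistic matters.** The chance that the point estimate is at or below the limit is P(χ² with 25 df ≤ 25 × (limit / true value)²). With a true SD of differences of 15%:

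| Statistic | True value | 25 × (15 / true)² | Chance at 15% | Chance at 10% |
|---|---|---|---|---|
| Within-subject CV | 10.6% | 50 | 99.8% | 38% |
| SD of differences | 15% | 25 | 54% | 0.8% |
| CR | 29.4% | 6.5 | under 0.01% | under 0.01% |

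If 15% is per-scan error, the chances at a 15% limit are 54%, 1.8% and under 0.01%.

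**4. Precision that 26 patients do give.** The 95% confidence interval for an SD runs from 0.784 to 1.380 times the estimate (chi-square, 25 df). An SD of differences of 15% has an interval of 11.8 to 20.7%, so a CR of 29.4% has 23.1 to 40.6%. With n = 30 the intervals are 11.9 to 20.2% and 23.4 to 39.5%. The plan states none of these.

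**The case against.** **The limit may not be a CR.** The hypothesis and Section 5 use the same two figures, 10 and 15, and Section 5 calls the second a variability. The nearest reading is that the limit is itself a variability, with 15% at its upper end. This stands. Read as within-subject CV or SD of differences, target and planning value are compatible. Read as mean bias, there is no conflict either, although a non-significant difference would still not show that bias lies within a limit.

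A reader might infer from CR being the only spread statistic named that the plan sets a limit its own 15% cannot meet. The documents do not support that. No section ties the limit to CR, and the 15% is described as the high end of PET variability, so it is a cautious sizing input and not a forecast of the result. What can be said is that a CR of 15% would need a spread about half the planning value (7.7 / 15).

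**The sample does inform repeatability.** It is also tempting to say that 26 patients support only the bias test. Objective 2 in Section 2 is to determine reproducibility, which is estimation, and step 4 shows that CR can be estimated. The gap is in the stated justification, not in the data to be collected.

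**The chances in step 3 assume a rule.** They treat the point estimate as the criterion, which the protocol does not say. They illustrate how much the missing definition matters and do not predict the outcome. Likewise, the one-sided test in step 1 is inferred from the arithmetic, so the sponsor must say what was intended.

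**Conclusion.** The point holds in this form: hypothesis 2 cannot be judged as written, and the power quoted for it belongs to a different question. Two findings do not depend on how the limit is read. First, no statistic or single limit is named. Second, the 0.95 is power for a 10% mean shift, and only if the test is one-sided with 15% as the SD of differences. Otherwise the power at n = 26 is 0.904, 0.756 or 0.637.

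A third finding is conditional. If CR is meant, and is defined as 1.96 × SD of differences, the planning value implies about 29% (about 42% if 15% is per-scan error) against a limit of 10 to 15%. On a CV or SD-of-differences reading this tension disappears.

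The size of the problem is best seen in the range of verdicts available from the same 26 patients at a 15% limit: almost certain success on CV and almost certain failure on CR. All figures rest on roughly normal percent differences.

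**What to change.** 1. State hypothesis 2 on one named spread statistic, with one limit on a stated scale (percent or log differences). The sponsor should choose both before analysis and keep them compatible with the planning value. For conversion, a CV of 10 to 15% corresponds to a CR of 27.7 to 41.6%.
2. Report bias and CR with 95% confidence intervals, and judge hypothesis 2 on the chosen spread statistic, not on a non-significant bias test.
3. In Section 5, relabel the 0.95 as power for a 10% mean difference, and state the sidedness and what the 15% measures. If the test is two-sided with 15% as the SD of differences, correct the power to about 0.90. Add the expected precision of the SD of differences or CR, as in step 4 of the working.

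The cost is rewording hypothesis 2 (Section 1.2 and Synopsis), the Phase 2 analysis sentence and the sample-size paragraph. Enrolment does not change. The downside is that the stated power and precision will look less favourable.

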For the correlation studies (hypothesis 1 and 3), two specific populations including 1) 30 participants with an intermediate to high probability of CAD (Phase 1) and 2) 30 healthy volunteers without known heart disease (Phase 3).

For the reproducibility study (hypothesis 2), 30 participants with an intermediate to high probability of CAD (Phase 2).

Inclusion and Exclusion Criteria**Inclusion Criteria****For all participants**

- Age \geq 18 years old
- BMI \leq 40 kg/m²
- Able and willing to comply with the study procedures

1. Participants with an intermediate to high probability of CAD
 - Suspected or known CAD on a stable medication regime
2. Healthy volunteers without known heart disease OR
 - Low risk of CAD (ACC Guidelines Pre-test Probability of CAD by Symptoms, Gender and Age)

Exclusion Criteria:

- History or risk of severe bradycardia (heart rate < 50 beats per minute) not related to chronotropic drugs

- Known second- or third-degree AV block without pacemaker
- Dyspnea (NYHA III/IV), wheezing asthma or severe COPD
- Coronary artery bypass graft (CABG) surgery within 60 days prior to screening or at any time after consent
- Percutaneous coronary intervention (PCI) within 30 days prior to screening or at any time following consent
- Acute myocardial infarction or acute coronary syndrome within 60 days prior to screening or at any time following consent
- Recent use of dipyridamole-containing medications (e.g. Aggrenox)
- Known hypersensitivity to dipyridamole
- Breastfeeding or pregnancy
- Claustrophobia or inability to lie still in a supine position
- Unwillingness or inability to provide informed consent

Study Duration for Participants Duration of participation is a maximum of 4 weeks. No changes to clinical care in the CAD population will be made.

Safety and Tolerability Safety variables will include the recurrence of procedure related adverse events. Adverse events (AE) and serious adverse events (SAE) will be defined and reported according to regulatory standards. AEs and SAEs will be reported from the signing of the consent and followed until resolution or determined to be not clinically significant.

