6.2 Inclusion Criteria

For all participants

- Age \geq 18 years old
- BMI \leq 40 kg/m²
- Able and willing to comply with the study procedures

Participants with intermediate to high probability of CAD

- Suspected or known CAD on a stable medication regime.

Healthy volunteers without known heart disease

- Low risk of CAD (ACC Guidelines Pre-test Probability of Coronary Disease by Symptoms, Gender and Age)

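### Phase 3 applies the same range-dependent r > 0.6 to low-risk volunteers as to CAD patients, with no agreement analysis to show whether a low r reflects SPECT error or a narrow flow range

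*Combined protocol and SAP*

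**What the plan says.** - **Same target for both populations.** Section 1.2, repeated in the Synopsis, gives for patients "using SPECT to PET in participants with an intermediate to high probability of CAD will be $r > 0.6$ (Phase 1" and for volunteers "calculated MFR using SPECT to PET in normal volunteers will be $r > 0.6$ (Phase 3".
- **One sample-size argument for hypotheses 1 and 3.** Section 5 asks for a "95% confidence interval around $r=0.6$ that excludes $r=0.25$, which is considered the upper bound of no correlation". It states that a "difference in the z-transform of $r=0.6$ and $r=0.25$ of 1.96 requires an n of 24", and then "A withdrawal rate of 10 to 15 % increases the number of patients required to 30 per group". The Synopsis accordingly plans "30 healthy volunteers without known heart disease (Phase 3".
- **How volunteers are chosen.** Section 6.2 requires "Low risk of CAD (ACC Guidelines Pre-test Probability of Coronary Disease by Symptoms, Gender and Age". No criterion refers to measured flow.
- **Analysis.** Section 5 and the Synopsis plan Spearman correlation for Phases 1 and 3. Bland-Altman bias and repeatability appear for Phase 2 only.
- **Error size.** The only measurement variability quoted is 15% in the Phase 2 sample size, "assuming a SPECT MBF uncertainty similar to the high end of PET variability". Section 5 does not say whether this is per scan or the SD of a difference.

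The documents give no expected mean, SD or range of flow for either population and no reason why 0.6 suits both. They do not say whether rest and stress MBF are correlated separately or together, or whether r > 0.6 refers to the estimate or to a confidence limit.

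**The concern.** Two methods with fixed measurement error correlate strongly in people whose true flows differ widely and weakly in people whose flows are alike. Using ranks does not remove this dependence. Phase 1 should include people with low stress flow and low MFR. Phase 3, by selecting for low CAD risk, leaves out those most likely to supply such values. The same camera, tracer and software could then give r above 0.6 in one phase and below it in the other.

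With Spearman as the only analysis, the report would hold nothing to separate inaccurate SPECT in normal hearts from a homogeneous sample. The supporting correlations in Section 1.1 (0.75 to 0.83 for MBF, up to 0.89 for MFR) do not settle the matter. They come from pigs studied at rest and with transient occlusion at stress, compared with microspheres, so the flow range there was widened by design.

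**Working it through.** **1. The plan's own figure.** Fisher z: atanh(0.6) − atanh(0.25) = 0.6931 − 0.2554 = 0.4377. Then n = (1.96/0.4377)² + 3 = 23.05, rounded up to 24, as stated. For withdrawal, 24/0.90 = 26.7 (27) and 24/0.85 = 28.2 (29), so 30 per group is consistent. The calculation assumes r = 0.6 in both populations.

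**2. Effect of a narrower range.** Assume one value per person, classical error, and the same error SD in both phases and both methods. With true variance V and error variance E, r = V/(V + E). If the Phase 1 correlation is r0 and the volunteers' between-person SD is u times the patients',

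r_vol = u²·r0 / (u²·r0 + 1 − r0).

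Example: r0 = 0.75 and u = 0.75 give 0.5625 × 0.75 = 0.4219, and 0.4219/(0.4219 + 0.25) = 0.63.

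r_vol falls below 0.6 when u < √[1.5(1 − r0)/r0]. The u values are assumptions; the 0.75 to 0.89 values of r0 are the pig results.

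| Phase 1 r0 | u = 0.75 | u = 0.50 | r_vol < 0.6 when u is below |
|---|---|---|---|
| 0.60 | 0.46 | 0.27 | 1.00 |
| 0.75 | 0.63 | 0.43 | 0.71 |
| 0.83 | 0.73 | 0.55 | 0.55 |
| 0.89 | 0.82 | 0.67 | 0.43 |

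The 0.60 row is the boundary case, where any narrowing takes r below 0.6.

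**3. In absolute terms.** With between-person CV t and error CV s for each method, r = t²/(t² + s²), and r = 0.6 needs t = s·√1.5.

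- If the 15% in Section 5 is per method: t = 15 × 1.225 = 18.4%.
- If it is the SD of a difference: s = 15/√2 = 10.6% and t = 13.0%.
- For MFR with independent rest and stress errors, s is multiplied by √2, giving 26% and 18%.

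Simulation of 30 pairs (bivariate normal, 20,000 runs) with s = 15%:

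| Between-person CV | True r | Chance that Spearman > 0.6 | Chance that 95% CI excludes 0.25 |
|---|---|---|---|
| 30% | 0.80 | 96% | 98% |
| 20% | 0.64 | 56% | 68% |
| 15% | 0.50 | 20% | 29% |
| 10% | 0.31 | 3% | 5% |

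**4. If rest and stress MBF are pooled.** Assume stress flow is 2 to 3 times rest, between-person CV is 10 to 20%, and error is 10.6 or 15%. Take the lowest case: ratio 2, CV 10%, error 15%, rest mean 1. True variance is 0.25 (between states) + (0.01 + 0.04)/2 = 0.275. Error variance is (0.0225 + 0.09)/2 = 0.05625. So r = 0.275/0.33125 = 0.83. The highest case (ratio 3, CV 20%, error 10.6%) gives 1.2/1.25625 = 0.96. Pooled MBF would then exceed 0.6 in volunteers, mainly because stress differs from rest. MFR already combines the two states and cannot be pooled in this way.

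**The case against.** A reader might infer that volunteers are chosen to have uniformly normal flow and that hypothesis 3 is therefore set up to fail. The documents do not support that.

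- Section 6.2 selects on CAD risk. It sets no flow criterion and no upper age limit, and BMI may reach 40. Phase 1 takes suspected as well as known CAD, so it may include many people with normal flow. A narrower volunteer range is a reasonable inference, not a documented fact.
- The size depends on the starting point. At Phase 1 correlations of 0.75, 0.83 and 0.89, a volunteer SD of 75% of the patients' still leaves r at 0.63, 0.73 and 0.82.
- The CV thresholds depend on the error assumptions. With PET error of 10% instead of 15%, the MBF threshold falls from 18.4% to 15.4%. With a correlation of 0.5 between rest and stress errors, the MFR threshold falls from 26% to 18.4%.
- If rest and stress MBF are pooled, the narrow range need not cost MBF anything.
- No pass/fail rule is stated. The sample size aims to exclude 0.25, and no comparison of Phase 3 with Phase 1 is planned.

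All of this stands, and it limits the claim to what could happen. It does not supply the missing analysis. MFR is named in hypothesis 3 and gains nothing from pooling. A high pooled r for MBF would say little about accuracy within a state. And r > 0.6 remains the only figure against which Phase 3 can be read.

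**Conclusion.** The point holds as a gap in the analysis, not as proof that Phase 3 will miss its target. One range-dependent threshold is applied to two populations without justification for the second, and no measure of SPECT-PET agreement is planned in either. Under equal error and assumed SD ratios of 75% and 50%, the expected volunteer r runs from 0.73 and 0.55 (Phase 1 r of 0.83) down to 0.46 and 0.27 (Phase 1 r of 0.60). The last value is close to the 0.25 that Section 5 sets out to exclude.

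The conclusion rests on a narrower volunteer range, which the documents neither state nor rule out. It applies most clearly to MFR and to rest or stress MBF analysed alone. It does not justify dropping the correlation objective.

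**What to change.** In Section 5:

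- Extend the Bland-Altman analysis from Phase 2 to the paired SPECT-PET data of Phases 1 and 3. Report bias, SD of differences and limits of agreement with 95% CIs, on absolute and percent scales, separately for rest MBF, stress MBF and MFR.
- Keep the Spearman correlation, but report it by state with its 95% CI and each phase's between-person SD.
- State that a volunteer r below 0.6 will not, on its own, be read as poor SPECT accuracy.
- Show the Phase 3 to Phase 1 ratio of the SDs of differences descriptively only. With 26 pairs per group and equal true SDs, its 95% CI is about 0.67 to 1.49, too wide to show that one SD is no larger than the other. On the percent scale it would also shift with mean flow if error is constant in absolute terms.

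The cost is a little more analysis on scans already planned, with no extra participants or imaging. The limits of agreement will be imprecise. The standard error of each limit is about SD × √(3/n), so the 95% half-width is 1.96 × √(3/26) = 0.67 SD with 26 pairs and 1.96 × √(3/30) = 0.62 SD with 30.
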